4.2 Accountability Records for Investigational Product(s)

UCSF Investigational Drug Services (IDS) will manage drug accountability records for UCSF.

4.3 Ordering Investigational Product(s)

UCSF will obtain daratumumab directly from pharmaceutical company and azacitidine as commercial supply.

5 Treatment Plan

5.1 Dosage and Administration

Treatment will be administered on an outpatient basis.

Daratumumab

Preparation

Daratumumab-SC will be provided as a fixed-dose (1800 mg), combination drug product containing rHuPH20 drug substance (2000 U/mL) and daratumumab drug substance (120 mg/mL) in a single vial. Manuals with detailed descriptions for preparation and administration of daratumumab will be supplied to the pharmacy and site.

Treatment Schedule and Administration

Daratumumab SC should be given according to product information: [REDACTED]

Daratumumab (1800 mg) will be administered by SC injection by manual push over approximately 3 – 5 minutes in the abdominal subcutaneous tissues in the left/right locations, alternating between individual doses. The volume of the SC solution will be 15 mL for the 1800 mg dose. Reasons for continued observation after daratumumab injection may include but are not limited to the following: subjects with a higher risk of respiratory complications (e.g., subjects with mild asthma or subjects with COPD who have an FEV1 < 80% at screening or developed FEV1 < 80% during the study without any medical history), subjects with IRR with the first injection of study drug, subject with decreased condition on day of dosing compared to prior dosing day. The dose of daratumumab will remain constant throughout the study.

All administration will be planned as outpatient visits. Subjects will receive pre-injection medications and post-injection medications as detailed in the protocol.

Daratumumab will be administered weekly during induction treatment in Cycles 1 to 2 (Days 1, 8, 15, 22), every 2 weeks during consolidation treatment in Cycles 3 to Cycle 6 (Day 1, 15), and every 4 weeks during maintenance treatment in Cycle 7 (Day 1) and beyond. This schedule is provided below in Table 5-1.

Table 5-1. Daratumumab Administration Schedule

Weeks	Cycle (every 4 weeks)	Schedule
Weeks 1 to 8 (induction)	Cycle 1-2	weekly (total of 8 doses)
Weeks 9 to 24 ^a (consolidation)	Cycle 3-6	every two weeks (total of 8 doses)
Weeks 25 onwards until disease progression ^b (maintenance)	Cycle 7 and onwards	every four weeks

^a First dose of the every-2-week dosing schedule is given at week 9

^b First dose of the every-4-week dosing schedule is given at week 25

As noted in the Study Procedures and Schedule of Events, vital signs should be monitored extensively on Cycle 1, Day 1 before, during, and after the first administration of daratumumab. For all other administrations, vital signs should be measured before the start of the injection and at the end of the injection. These vital signs will be measured by standard daratumumab subcutaneous protocol. If a subject experiences any significant medical event, then the investigator should assess whether the subject should stay overnight for observation. If the subject has not experienced a significant medical event but is hospitalized overnight only for observation, then the hospitalization should not be reported as a serious adverse event.

If an IRR develops, then the injection should be temporarily interrupted or slowed down. In the event of a life-

threatening IRR (which may include pulmonary or cardiac events) or anaphylactic reaction, dara-SC should be discontinued, and no additional dara-SC should be administered to the participant. See section below for instructions on the management of IRR and local ISRs.

Guidelines for Prevention and Management of Administration-Related Reactions and Local Injection-site Reactions of Daratumumab-SC

Pre-dose Medication

All participants will receive the following medications 1 to 3 hours prior to each study drug administration:

- An antipyretic: paracetamol (acetaminophen) 650-1000 mg IV or PO
- An antihistamine: diphenhydramine 25-50 mg IV or PO or equivalent. Avoid IV use of promethazine.
 - After Cycle 6, if a participant has not developed an administration-related reaction and is intolerant to antihistamines, modifications are acceptable as per investigator discretion.
- Corticosteroids (Long-acting or intermediate-acting):
 - *Dexamethasone dosing as part of combination therapy:*
 - Administer 40 mg dexamethasone (or equivalent) prior to every daratumumab injection in the first two cycles. Since dexamethasone is also the background regimen specific corticosteroid for this treatment regimen, the dexamethasone treatment dose will instead serve as pre-medication on daratumumab administration days.
 - Dexamethasone is given orally or intravenously prior to the first daratumumab injection and oral administration may be considered prior to subsequent injections.
 - If the subject does not experience a major systemic administration-related reaction after the first 8 doses of daratumumab, consider discontinuing the administration of corticosteroids as a pre-medication (excluding any background regimen-specific corticosteroid or treatment-specific dexamethasone as determined by the primary treating provider).
 - Further dose reduction of dexamethasone is permitted based on dose modification criteria outlined in [Section 5.5](#).

Pre-dose administration of a leukotriene inhibitor (montelukast 10 mg PO or equivalent) is optional in Cycle 1 Day 1 and can be administered up to 24 hours before administration as per investigator discretion.

If necessary, all PO pre-administration medications may be administered out of the clinic on the day of the administration, provided they are taken within 3 hours before the administration.

Post-dose Medication

Administer post-dose medication to reduce the risk of delayed administration and injection related reactions as follows:

- Consider administering low-dose methylprednisolone (≤ 20 mg) or equivalent, the day after the administration.
- For participants with a higher risk of respiratory complications (e.g. participants with mild asthma or participants with COPD who have an FEV1 $< 80\%$ at screening or developed FEV1 $< 80\%$ during the study without any medical history) the following post-administration medication should be considered:
 - Antihistamine (diphenhydramine or equivalent)
 - Leukotriene inhibitor (montelukast or equivalent)
 - Short-acting $\beta 2$ adrenergic receptor agonist such as salbutamol aerosol
 - Control medications for lung disease (e.g. inhaled corticosteroids \pm long-acting $\beta 2$ adrenergic

receptor agonists with asthma; long-acting bronchodilators such as tiotropium or salmeterol ± inhaled corticosteroids for participants with COPD)

- Investigators may prescribe bronchodilators, H1-antihistamines, and corticosteroids that are deemed necessary to provide adequate supportive care in the event a bronchospasm occurs after participants are released from the hospital/clinic. If an at-risk participant experiences no major administration-related reactions, then these post-administration medications may be waived after 4 doses at the investigator's discretion.
- Any post-injection medication will be administered after the injection has completed.

Management of Administration-related Reactions and Local Injection-site Reactions of Daratumumab-SC

Injection-related Reactions (IRRs)

Injection-related reactions (IRRs) are systemic reactions related to daratumumab administration. Participants should be observed carefully during daratumumab administrations. Trained study staff at the clinic should be prepared to intervene in case of any IRRs, and resources necessary for resuscitation (e.g., agents such as epinephrine and aerosolized bronchodilator, medical equipment such as oxygen tanks, tracheostomy equipment, and a defibrillator) must be available at the bedside. Attention to staffing should be considered when multiple participants will be dosed at the same time. If an IRR develops during Dara SC administration, then the administration should be temporarily interrupted. Participants who experience AEs during Dara-SC administration must be treated for their symptoms. Participants should be treated with paracetamol (acetaminophen), antihistamine, or corticosteroids, as needed. Intravenous saline may be indicated. For bronchospasm, urticaria, or dyspnea, participants may require antihistamines, oxygen, corticosteroids, or bronchodilators. For hypotension, participants may require vasopressors. In the event of a life-threatening IRR (which may include pulmonary or cardiac events) or an anaphylactic reaction, Dara-SC should be discontinued.

Injection-related Reactions Grade 1 or Grade 2:

If the investigator assesses a Grade 1-2 IRR to be related to administration of study intervention, then the Dara-SC administration should be interrupted. When the participant's condition is stable, Dara-SC administration may be restarted at the investigator's discretion. Refer to the SIPPMM for further details regarding continuation of Dara-SC administration.

If the participant experiences a Grade 2 or higher event of laryngeal edema, or a Grade 2 or higher event of bronchospasm that does not respond to systemic therapy and does not resolve within 6 hours from onset, then the participant must be permanently discontinued from Dara-SC treatment.

Injection-related Reactions Grade 3 or Higher:

For IRR AEs (other than laryngeal edema or bronchospasm) that are Grade 3, the Dara-SC administration must be stopped, and the participant must be observed carefully until resolution of the AE or until the intensity of the event decreases to Grade 1, at which point the Dara-SC administration may be restarted at the investigator's discretion. Refer to the SIPPMM for further details regarding continuation of Dara-SC administration.

If the intensity of the AE returns to Grade 3 after restart of the Dara-SC administration, then the participant must be permanently discontinued from Dara-SC treatment.

For IRR AEs that are Grade 4, the Dara-SC administration must be stopped, and the participant permanently discontinued from Dara-SC treatment.

Recurrent Injection-related Reactions:

If a Grade 3 IRR (or Grade 2 or higher event of laryngeal edema, or a Grade 2 or higher event of bronchospasm) recurs during or within 24 hours after a subsequent Dara-SC administration, the participant must be permanently discontinued from Dara-SC treatment.

Injection Site Reactions:

In clinical studies, SC administration of daratumumab was associated with local injection site reactions, such as induration and erythema, in some subjects. The reactions usually resolved within 60 minutes. Local injection-site reactions should be managed per institutional standards.

Recommended Concomitant Therapy:

- Prophylaxis for Herpes Zoster Reactivation:
 - Prophylaxis for herpes zoster reactivation is recommended during the Treatment Phase, as per institutional guidelines. Initiate antiviral prophylaxis to prevent herpes zoster reactivation within 1 week after starting study treatment and continue for 3 months following study treatment. Acceptable antiviral therapy includes acyclovir (eg 400 mg given orally 3 times a day, or 800 mg given orally 2 times a day or per institutional standards), famcyclovir (eg, 125 mg given orally, twice a day or per institutional standards), or valacyclovir (eg, 500 mg given orally, twice a day or per institutional standards), initiated within 1 week after the start of study drug.
- Management of Hepatitis B Virus Reactivation:
 - Primary antiviral prophylaxis is permitted as per local standard of care. Per protocol, HBV DNA testing by PCR is mandatory for participants at risk for HBV reactivation.
 - In patients who develop reactivation of HBV while on study treatment, suspend treatment with study treatment and any concomitant steroids, chemotherapy, and institute appropriate treatment. Resumption of study treatment in patients whose HBV reactivation is adequately controlled should be discussed with physicians with expertise in managing HBV.

Azacitidine

Azacitidine should be given at 75mg/m² IV/SC for 5 consecutive days starting in cycle 1 day -7 to -3. Subsequently azacitidine will be given for 5 consecutive days on days 22-26 of cycles 1-3. Patients should be premedicated for nausea and vomiting. Cycles should be repeated every 4 weeks with dose modifications as needed per parameters outlined below in [Section 5.5.2.1](#). Starting cycle 5, azacitidine will be given for 5 consecutive days on days 1-5 to coordinate with daratumumab dosing. This protocol uses azacitidine 5 day dosing as opposed to the standard 7 day dosing used in MDS and AML, given that studies have shown equivalent efficacy with 5 day dosing and we hope to minimize cumulative toxicities.³⁹ Treatment may be continued as long as the patient continues to benefit.

Dexamethasone

Dexamethasone at a dose of 40 mg PO (or IV if PO is not available) will be given weekly for Cycle 1 and 2. This dose may be reduced or stopped after Cycle 2 on both non-daratumumab administration weeks and as a pre-medication on daratumumab administration weeks as per treating physician discretion. Further dose reduction is permitted based on dose modification criteria outlined in [Section 5.5](#).

Subjects may receive low-dose methylprednisolone (≤ 20 mg) orally (or equivalent in accordance with local standards) for the prevention of delayed IRRs as clinically indicated.

Dose modifications, dose delays, and dose interruptions for study drugs are described in [Section 5.5](#).

5.2 Treatment Compliance

Study drug (daratumumab) will be administered as a subQ injection and study drug (azacitidine) will be administered either as IV or subQ by qualified staff and the details of each administration will be recorded in APEX, the electronic medical record system used at UCSF. Additional details are provided in the study site investigational product and procedures manual. Subjects will be provided with a diary to record intake of dexamethasone; sites will use information to complete exposure information in the CRF. The drug diary will be returned to clinic staff at the end of each month.

Table 5-2. Regimen Description

Investigational Product	Premedication; precautions	Dose	Route	Schedule	Cycle Length
Daratumumab	Pre-medication with corticosteroid, acetaminophen, diphenhydramine, and monteleukast 1-3 hours prior to administration (See section 5.1.1.3 for further details)	1800 mg	SC	D1, D8, D15, D22 for Cycle 1-2 D1, D15 Cycle 3-6 D1 Cycle 7 and onwards	Every 4 weeks
Azacitidine	Premedicate with antiemetics	75 mg/m ² or MTD	IV/SubQ	Day -7 to Day -3 Cycle 1, Day 22-26 Cycle 1-3, Day 1-5 Cycle 5 and onwards	
Dexamethasone	Take prior to daratumumab administration on days of daratumumab administration and may also be given weekly on weeks without daratumumab	40 mg (or lower after Cycle 2)	PO	Dexamethasone 40 mg PO (or IV if PO is not available) weekly for Cycle 1 and 2. This dose may be reduced or stopped after Cycle 2 both on non-daratumumab administration weeks and on daratumumab administration weeks (as pre-medication). Further dose reduction is permitted based on dose modification criteria outlined in Section 5.5 .	

See Dosing Schedule Diagram in [Section 3.1](#).

5.3 Other Investigational Procedures/Modalities

There will be no other investigational procedures/modalities (e.g surgery, radiotherapy, hematopoietic stem cell transplantation) used in the protocol study treatment, if applicable.

5.4 Dose Limiting Toxicity

Dose-limiting toxicities are defined as the following toxicities if they occur anytime within the first 5 weeks of starting azacitidine (anytime within Cycle 1) and are thought to be secondary to azacitidine in combination with daratumumab:

- Grade 4 neutropenia lasting more than 7 days.
- Grade 4 thrombocytopenia lasting more than 7 days despite transfusion support.

- Grade 3 or higher non-hematological toxicity except:
 - Grade 3 nausea, vomiting or diarrhea that can be controlled within 48 hours with maximal supportive care.
 - Grade 3 hyperglycemia that can be controlled within 48 hours with appropriate supportive care.
 - Asymptomatic new Grade 3 or higher electrolyte disturbances that can be controlled with repletion or other medical management within 24 hours.

Severity of AEs will be graded according to CTCAE Version 5.0. As described in [Section 8.2.2](#), interim analysis will occur after accrual of 6 patients in the safety cohort. Study accrual will be stopped until these 6 patients have completed at minimum 5 weeks of treatment after starting azacitidine (ie completed Cycle 1), at which point a formal interim safety analysis will be performed with assessment for DLTs as defined above and safety stopping bounds for DLTs as described in [Section 8.2.2](#). Guidelines for dose reductions of azacitidine due to toxicity or dose delays/holding for daratumumab toxicity are detailed in [Section 5.5](#).

5.5 Dose Modifications and Dosing Delays

Daratumumab

Dose Modification

No daratumumab dose modification (increase or decrease) will be permitted unless the subject's weight changes more than 10% from Cycle 1 Day 1 or the most recent weight used for dose calculation. Subject's weight will be recorded on all daratumumab dosing days.

Daratumumab-Related Toxicity Management and Dose Delay

ONLY if any of the following criteria are met and the event cannot be attributed to azacitidine, or underlying multiple myeloma, the daratumumab administration must be held to allow for recovery from toxicity. The criteria for a dose delay are:

- Grade 4 hematologic toxicity (except for Grade 4 lymphopenia), or Grade 3 or higher thrombocytopenia with bleeding
- Febrile neutropenia of any grade
- Grade 4 Neutropenia with any grade infection
- Grade 3 or higher non-hematologic toxicities with the following exceptions:
 - Grade 3 nausea or Grade 3 vomiting that responds to antiemetic treatment within 48 hours of supportive care
 - Grade 3 diarrhea that responds to antidiarrheal treatment within 48 hours of supportive care
 - Grade 3 fatigue or asthenia that was present at baseline and lasts for <7 days after the last administration of daratumumab
 - Grade 3 or 4 electrolyte disturbances which can be managed with replacement therapy

If daratumumab administration does not commence within the prespecified window of the scheduled administration date, then the dose will be considered a missed dose. See Table 5-3 Daratumumab-Related Dose Delay Time Chart.

Administration may resume at the next planned dosing date. See [Section 5.5.1.4](#), Interruption or Missed Doses for additional information.

Table 5-3 Daratumumab-Related Dose Delay Time Chart

Weeks	Frequency	Missed Dose	Dosing Resumption
Weeks 1-8 (induction)	Weekly	≥ 3 days	Next planned weekly dosing date
Weeks 9-24 (consolidation)	Every 2 weeks	≥ 14 days	Next planned every 2 week dosing date
Week 25 onwards until disease progression (maintenance)	Every 4 weeks	≥ 14 days	Next planned every 4 week dosing date

A missed dose will not be made up. Any adverse event listed above deemed to be related to daratumumab that requires a dose hold of more than 3 doses will result permanent discontinuation of daratumumab and patient's withdrawal from this study.

Dose Delay

A dose is deemed to have been delayed if the treatment is 2-3 days beyond the theoretical day of treatment for weekly dose, 3-14 days beyond the theoretical day of treatment for Q2W dose, and 4-14 days beyond the theoretical day of treatment for Q4W dose. The reason for dose delay will be captured.

Interruption or Missed Doses

A daratumumab dose held for more than 3 days during induction, 14 days during consolidation, or 14 days during maintenance from the per protocol administration date for any reason other than toxicities suspected to be related to daratumumab should be brought to the attention of the sponsor at the earliest possible time. Subjects who miss ≥ 3 consecutive planned doses of daratumumab for reasons other than toxicity will be withdrawn from treatment, unless, upon consultation with the sponsor and the review of safety and efficacy, continuation is agreed upon.

Azacitidine

Dose modification

The dose for azacitidine can be reduced as follows, based on counts for any given cycle:

Table 5-4 Dosage Adjustment for Azacitidine Based on Hematology Laboratory Values:

Counts		% Dose Administered in the Next Cycle
ANC ($\times 10^9/L$)	Platelets ($\times 10^9/L$)	

<0.5 (Gr 4)	<25 (Gr 4)	50%
0.5 – 1.5 (Gr 2-3)	25-50 (Gr 3)	67%
> 1.5 (Gr 0-1)	> 50 (Gr 0 -2)	100%

Dosage Adjustment Based on Renal Function and Serum Electrolytes during treatment (not at baseline):

If unexplained reductions in serum bicarbonate levels to less than 20 mEq/L occur, the dosage should be reduced by 50% on the next cycle. Similarly, if unexplained elevations of BUN or serum creatinine occur, the next cycle should be delayed until values return to normal or baseline and the dose should be reduced by 50% on the next treatment cycle.

Use in Geriatric Patients:

Azacitidine and its metabolites are known to be substantially excreted by the kidney, and the risk of toxic reactions to this drug may be greater in patients with impaired renal function. Because elderly patients are more likely to have decreased renal function, care should be taken in dose selection, and it may be useful to monitor renal function.

For any other non-hematologic \geq grade 3 AE thought to be secondary to azacitidine, dose should be held until recovery defined as improvement to at least grade 1, and resumed at 50% dose on the next treatment cycle. If non-hematologic \geq grade 3 AE or hematologic \geq grade 4 AE lasting more than 7 days thought to be secondary to azacitidine occurs at azacitidine dose $< 25 \text{ mg/m}^2$, then azacitidine will be stopped and patient will withdraw from study. Guidelines for DLTs within the first cycle (ie within the first 5 weeks of starting azacitidine) are detailed in [Section 5.4](#).

Further dose modifications or dose delays for azacitidine based on adverse events during treatment will be left to the discretion of the treating provider. In the event that the investigator feels deviation from the recommendations above is required, please consult the study chair to discuss for approval.

If the dose of azacitidine is reduced, at the investigator's discretion, the dose of azacitidine may be re-escalated after 2 cycles of a dose reduction in the absence of a recurrence of the toxicity that led to the reduction. Dose changes must be recorded in the Dose Administration eCRF.

Dose Delay

A dose is deemed to have been delayed if the treatment is ≥ 4 days beyond the theoretical day of treatment for this Q4W dose. The reason for dose delay will be captured.

Interruption or Missed Doses

An azacitidine dose held for more than 2 times for any reason other than toxicities suspected to be related to azacitidine will be reviewed by the study team at the earliest possible time. Subjects who miss ≥ 3 consecutive planned doses of azacitidine for reasons other than toxicity will be withdrawn from treatment. Any missed dose of azacitidine will not be made up.

The following dose modification rules will be used with respect to potential toxicity. Toxicity will be assessed according to the NCI CTCAE version 5.0.

If a participant experiences several adverse events and there are conflicting recommendations, the investigator should use the recommended dose adjustment that reduces the dose to the lowest level.

Table 5-5. Dose Modifications and Dosing Delays Tables for Specific Adverse Events

Dose modifications for AEs thought to be secondary to either drug, azacitidine or daratumumab, will be made as below:

Adverse Events: Neutropenia		
Grade of Event	Management/Next Dose for Azacitidine	Management/Next Dose for Daratumumab

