\leq Grade 1	No change	No change
Grade 2	No change	No change
Grade 3	Hold dose until recovery to at least Grade 1, then resume dose at 50%	Dose delay until recovery to at least Grade 1, can resume at same dose*
Grade 4	Hold dose until recovery to at least Grade 1, then resume dose at 50%	Dose delay until recovery to at least Grade 1, can resume at same dose*

*Toxicity criteria for holding daratumumab dose are detailed above in [Section 5.5.1.2](#)

** Participants having \geq Grade 3 AE at a dose $< 25 \text{ mg/m}^2$ should go off study

Dexamethasone

Dexamethasone Toxicity

For management of dexamethasone toxicity see table below. If dexamethasone is permanently discontinued due to toxicity, pre- and post-administration doses administered on the day of daratumumab dosing may be given at the investigators' discretion. This table represents suggested dose modifications of dexamethasone, but physician discretion and clinical judgment should prevail.

Table 5-6

NCI-CTCAE Category	Toxicity	Dose Change
Gastrointestinal	Grade 1-2 dyspepsia, gastric, or duodenal ulcer, gastritis requiring medical management	Treat with H2 blockers, sucralfate, or omeprazole. If symptoms persist despite above measure, decrease dexamethasone dose by 50%.
	≥Grade 3 requiring hospitalization or surgery	Hold dexamethasone until symptoms adequately controlled. Restart at 50% of current dose along with concurrent therapy with H2 blockers, sucralfate, or omeprazole. If symptoms persist despite above measure, discontinue dexamethasone and do not resume.
	Acute pancreatitis	Discontinue therapeutic dose of dexamethasone and do not resume.
Cardiovascular	≥Grade 3 edema limiting function and unresponsive to therapy or anasarca	Diuretics as needed and decrease dexamethasone dose by 25%. If edema persists despite above measures, decrease dose to 50% of initial dose. Discontinue dexamethasone and do not resume if symptoms persist despite 50% reduction.
Neurology/ Psychiatric	≥Grade 2 interfering with function but not interfering with activities of daily living	Hold dexamethasone until symptoms adequately controlled. Restart at 50% of current dose. If symptoms persist despite above measure, discontinue dexamethasone and do not resume.

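### Read literally, Table 5-5 halves azacitidine after a single Grade 3 daratumumab injection reaction, and its daratumumab column conflicts with the permanent stops in Section 5.1

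*Combined protocol and SAP*

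**What the plan says.** Table 5-5 is introduced with "Dose modifications for AEs thought to be secondary to either drug, azacitidine or daratumumab, will be made as below". It has blocks for neutropenia, thrombocytopenia, renal toxicity and other non-hematologic toxicity, and none for injection-related reactions. In the other non-hematologic block, the azacitidine entry at both Grade 3 and Grade 4 is "Hold dose until recovery to at least Grade 1, then resume dose at 50" percent. The daratumumab entry at both grades is "Dose delay until recovery to at least Grade 1, can resume at same dose". At Grade 2 neither drug changes.

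The azacitidine text above the table is narrower. It applies the hold and 50% resumption to a non-hematologic "grade 3 AE thought to be secondary to azacitidine, dose should be held until recovery". The daratumumab text (5.5.1.2) also works by attribution: only if "the event cannot be attributed to azacitidine, or underlying multiple myeloma, the daratumumab administration must be held".

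Section 5.1 defines injection-related reactions as related to daratumumab administration and gives them a graded algorithm. One rule reads: "For IRR AEs that are Grade 4, the Dara-SC administration must be stopped, and the participant permanently discontinued from Dara-SC treatment". Permanent discontinuation is also required for:
- a Grade 3 reaction that returns to Grade 3 on restart;
- a Grade 3 reaction, or Grade 2 or higher laryngeal edema or bronchospasm, that recurs during or within 24 hours after a later dose;
- Grade 2 or higher laryngeal edema, or Grade 2 or higher bronchospasm that does not respond to systemic therapy and does not resolve within 6 hours.

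Section 5.1 does not say what happens to azacitidine after such a reaction.

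**The concern.** One event falls under two rules that give different azacitidine doses, and nothing in Section 5.5 says which prevails. Azacitidine is the drug added to raise CD38, so staff who work from the table would halve it for a reaction it did not cause.

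The daratumumab column raises a different problem. For the reactions listed in Section 5.1, a table entry that permits resumption, or no change, sits against a rule that requires a permanent stop. Staff are directed towards the table: the dexamethasone part of Section 5.1 sends them to 5.5 for dose changes, and Section 5.6 refers to 5.5 for discontinuation reasons. Neither 5.5 nor 5.6 points back to the reaction stops.

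**Working it through.** **Which rule reaches a daratumumab injection reaction?**

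| Event | Table 5-5 | Other text |
|---|---|---|
| Azacitidine after a Grade 3 reaction | Hold, resume at 50% | 5.5 azacitidine text: cut only if thought secondary to azacitidine |
| Daratumumab after a Grade 4 reaction | Delay, can resume at same dose | 5.1: permanent stop |
| Daratumumab after a Grade 3 reaction that returns or recurs | Delay, can resume at same dose | 5.1: permanent stop |
| Daratumumab after Grade 2 laryngeal edema or unresolved bronchospasm | No change | 5.1: permanent stop |

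**Does anything in 5.5 settle the conflict?**
- The table's single-asterisk footnote sends the daratumumab column to 5.5.1.2. The azacitidine column has no matching pointer to its attribution limit.
- 5.5.1.2 mentions no injection-reaction stop. Its only permanent-stop rule is a hold of more than 3 doses.
- The tie-break begins "If a participant experiences several adverse events and there are conflicting recommendations". It covers several events, not one event under two rules.

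**Size of the azacitidine cut.** The plan states no figure to reproduce. The inputs are 75 mg/m2 for 5 days per course, given from Day -7 of Cycle 1, on Days 22-26 of Cycles 1-3, and on Days 1-5 from Cycle 5 (Section 5.1 and Table 5-2). Calendar footnote c lists Day 22 courses for Cycles 1-2 only; the Section 5.1 schedule is used here.

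- Full course: 75 × 5 = 375 mg/m2. Halved course: 375 × 0.5 = 187.5 mg/m2.
- Case: one non-recurrent Grade 3 reaction on Cycle 1 Day 1. The next course starts on Day 22, 22 − 1 = 21 days later, so the hold has probably ended and only the cut remains.
- Planned total through Cycle 3: 4 × 375 = 1,500 mg/m2.
- Re-escalated, since "the dose of azacitidine may be re-escalated after 2 cycles of a dose reduction": 375 + 187.5 + 187.5 + 375 = 1,125; 1,125/1,500 = 75%.
- Not re-escalated: 375 + 3 × 187.5 = 937.5; 937.5/1,500 = 62.5%.
- Under the azacitidine text: 1,500, or 100%.

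Over eight courses (through Cycle 8, near the anticipated 8 months of treatment), the planned total is 8 × 375 = 3,000. With re-escalation it is 3,000 − 2 × 187.5 = 2,625 (87.5%); without, 375 + 7 × 187.5 = 1,687.5 (56.25%).

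**Patients affected.** The documents give no Grade 3 or higher reaction rate for this population. Assuming 1% to 5%: 23 × 0.01 = 0.23 and 23 × 0.05 = 1.15 patients.

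**Endpoints.** The second marrow sample for CD38 is taken after the first azacitidine course and before the first daratumumab dose (Sections 3.1 and 6.4), so no daratumumab reaction can affect it. No input to the Simon design is involved.

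**The case against.** On azacitidine, the literal reading is arguably the less natural one. A lead-in naming either drug, followed by one column per drug, can be taken to mean that each column applies to its own drug's events. The azacitidine text and 5.5.1.2 both work that way. This stands as evidence of intent, but it does not remove the mismatch between table and text.

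A reader might infer that the only way to avoid the cut is to ask the study chair to approve a deviation. The documents do not support that. Following the azacitidine text is following the protocol, and the chair-approval clause refers to recommendations placed before the table. Further modifications are left to the treating provider, and re-escalation is at the investigator's discretion.

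A reader might also infer that the plan permits daratumumab again after a Grade 4 reaction. It does not. Section 5.1 is mandatory and specific, while the table only says that treatment can resume. Other text also bars re-exposure: Section 5.1 on life-threatening or anaphylactic reactions, the Section 4.1 contraindication, exclusion 9 together with Section 3.4, and the significant-toxicity ground in 5.6. Footnote b of the study calendar points to Section 5 as a whole, so the rule can be found. What remains is that 5.5 and 5.6 state no precedence and do not cite the reaction stops, although Section 5.9 cites the reaction-management text.

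Finally, a reader might extend the azacitidine problem to every Grade 3-4 reaction. A Grade 4 reaction ends daratumumab and with it the study combination, so the halving matters mainly for a single, non-recurrent Grade 3 reaction.

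**Conclusion.** The inconsistency is real and minor. Read literally, Table 5-5 halves the next azacitidine course after a single Grade 3 daratumumab injection reaction, against the section's own attribution rule. Its daratumumab column also conflicts with Section 5.1 for the reactions listed there. Section 5.1 should govern, so the daratumumab part is mainly a matter of clarity.

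For an affected patient, azacitidine through Cycle 3 would be 75% or 62.5% of plan, depending on re-escalation. This assumes the reaction occurs on Cycle 1 Day 1, has resolved by Day 22, and no other dose change is made. Probably no more than about one patient would be affected; that count rests on the assumed 1% to 5% rate. Known intolerance to daratumumab is an exclusion, and the background section reports fewer reactions with subcutaneous than with intravenous dosing, which both point to a low number. The error rates, sample size and CD38 endpoint do not change.

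**What to change.** 1. In the azacitidine column of the Table 5-5 non-hematologic rows, limit the 50% cut to events thought to be secondary to azacitidine.
2. State in Table 5-5, 5.5.1.2 and 5.6 that daratumumab injection-related reactions follow Section 5.1, including its permanent-discontinuation rules, and that Section 5.1 takes precedence over the table.
3. For these reactions, require no azacitidine dose reduction. If both drugs are due the same day (Day 22 of Cycles 1-2, Day 1 from Cycle 5), hold azacitidine until the reaction recovers to Grade 1 or less.

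Three wordings should be avoided. A blanket statement that azacitidine is unchanged at any grade would remove the hold during an unresolved same-day reaction. Listing injection reactions among the 5.5.1.2 exceptions would waive the daratumumab hold. The text should also not imply that azacitidine continues alone once daratumumab is permanently stopped, because the trial does not study that regimen.

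The cost is a few sentences at the next amendment. No visit, sample size or data item changes: administration reactions of Grade 3 or higher are already events of special interest in Section 7.3.
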